4. PHQ-9 –
 - i. Number of Questions – 9
 - ii. Time to Complete – 5 min

XV.Ocular Surface Evaluation Procedures

The evaluation procedures should be performed in the order specified below to minimize disruption of the ocular surface.

1. Tear Breakup Time

Two people are required to measure tear breakup time, one who does the examination and one who holds timer. The tear breakup time should be measured prior to instillation of any anesthetic drops. A dry fluorescein strip should be touched lightly to the tear meniscus, and the patient instructed to blink several times. After even distribution of the fluorescein, the patient should be asked to blink again and then hold the eye open. The instant the patient holds their eye open an assistant should start a stopwatch. The examiner will remain looking at the ocular surface with the cobalt blue light at the slit lamp, and signal to the timer when the first break in the tear film occurs. This should be repeated a total of three times, and all three times recorded.

2. Meibomian Gland Grading

Meibomian glands will be evaluated using the handheld Meibomian gland expression device (MGED)²⁵ using the procedure described in Meadows, et al.²⁶

Two areas of the lower lid will be used for Meibomian gland grading – the temporal lower lid from the 4th-9th observable Meibomian gland orifice (counting from the lateral canthus) and the central lower lid from the 15th- 20th Meibomian gland orifice (counting from the lateral canthus).

The first step is observation of the glands, with assignment of a morphology score (Table 2). Following this, the glands will be expressed using the MGED, and meibum quality score will be assigned (Table 2).

Lid Morphology	Assigned Grade	Meibum Quality
No plugged glands	0	Clear, fluid meibum
Mild (1-2 glands plugged)	1	Granular or yellowish meibum
Moderate (3-4 glands plugged)	2	Whitish, semi-solid meibum
Severe (5+ glands plugged)	3	Solid, toothpaste-like meibum
-	4	No expressible meibum

Table 2: Meibomian gland scoring system, adapted from Meadows, et al²⁶

3. Schirmer Testing

Schirmer testing will be performed using commercially available filter paper Schirmer strips. The strips should be placed at the outer canthus with the tip of the strip tucked between the lower lid and the bulbar conjunctiva, with both eyes being tested at the same time. The strips should be left in place for 5 minutes or until the length of the strip is saturated. The result should be recorded in mm of paper wetted by tears. No anesthetic drops should be given prior to testing.

4. SICCA Scoring

A drop of 0.25% fluorescein should be administered to the conjunctiva of each eye and the patient allowed to wait for approximately 5 minutes. Following this, the corneal epithelium should be examined for staining following the method of Whitcher, et al²⁷, and the number of punctate epithelial erosions (PEE) counted. A Lissamine green strip should then be saturated with 0.05% proparacaine and the proparacaine allowed to sit on the surface for 30 seconds, this should then be applied to the conjunctiva and the number of conjunctival PEE counted. A score will be assigned according to the following system, from Whitcher, et al²⁷. The scores will range from 0 (no staining) to 12 (severe dry eye findings).

SICCA Ocular Staining Score

[figure not shown]
Right Eye		Left Eye	
Staining pattern score:			
Lissamine Green (conjunctiva only)	Fluorescein (cornea only)	Lissamine Green (conjunctiva only)	Fluorescein (cornea only)
Grade	Dots	Grade	Dots
0	0-9	0	0
1	10-32	1	1-5
2	33-100	2	6-30
3	>100	3	>30
			
Extra points-fluorescein only: (Mark all that apply and add to fluorescein score)		Extra points-fluorescein only: (Mark all that apply and add to fluorescein score)	
 +1 - patches of confluent staining  +1 - staining in pupillary area  +1 - one or more filaments		 +1 - patches of confluent staining  +1 - staining in pupillary area  +1 - one or more filaments	
Total Ocular Staining score:		 	

Figure 1: SICCA scoring system²⁷

5. HD Analyzer

The HD Analyzer is a FDA approved device to measure ocular surface light scatter. As the tear film is the first surface that light encounters as it enters the eye, disruption of the tear film from Meibomian gland disease can have optical sequelae.

Subjects will receive HD Analyzer measurements of the OSI (ocular surface index) at enrollment, 1 month, and 3 month timepoints per manufacturer instructions.

XVI. Safety and Data Monitoring

a. Adverse Events

All adverse events will be recorded and reported via the Adverse Event Reporting Form (AERF, MOP), and entered into an Adverse Event Log for the patient (MOP). Below is a list of adverse events (AE) and serious adverse events (SAE).

Ocular Adverse Event	Non-Serious	Serious
Ocular Irritation	Mild to moderate irritation treatable with adjuvant lubricant drops.	Impairs patient's ability to complete activities of daily living, after normal surgical recovery period.
Ocular Hypertension	≥ 24 mm Hg	Surgery required (laser or incisional)
Subconjunctival hemorrhage	Subconjunctival hemorrhage greater than 5mm indiameter after injection	
Cataract	Visually significant cataract, cataract surgery indicated	
Infectious scleritis or keratitis		Any occurrence is a serious adverse event
Corneal or scleral perforation		Any occurrence is a serious adverse event

Systemic Adverse Event	Non-Serious	Serious
Nausea	Any nausea	Severe discomfort, minimal food intake for 3 or more days or at least a 2.5 kg weight loss resulting from nausea
Vomiting	Any vomiting	Severe: vomiting all food or fluids in 24 hours or orthostatic hypotension or at least a 2.5 kg weight loss resulting from vomiting
Diarrhea	Any diarrhea	Severe, bloody diarrhea or 8-9 loose stools in 24 hours or orthostatic hypotension or at least a 2.5 kg weight loss resulting from diarrhea
Dyspnea	Breathlessness on significant exertion or breathlessness at normal level of activity	Breathlessness at rest
Headache	Moderate, non-narcotic analgesic therapy required	Severe, requires narcotic therapy
Fatigue	Self-reported fatigue	Normal activity reduced >50%; cannot work or unable to care for self
Fever for 12 hours	> 100.6 to 103°F/39.5°C	≥ 103°F/39.5°C
Muscle strength	Subjective weakness, no objective symptoms or mild objective weakness, no decrease in function	Objective weakness, function limited, or worse

Mood	Self-reported mood changes or psychiatric diagnosis not requiring medical therapy (specify):	Psychiatric diagnosis requiring medical treatment or hospitalization
Cardiac function	Mild congestive heart failure (CHF) or arrhythmia not requiring treatment or moderate CHF or worse, arrhythmia requiring treatment, stable angina	Unstable angina, severe CHF, myocardial infarction, or arrhythmia requiring hospitalization
Neurologic function	Numbness or tingling	Total loss sensation
Allergic reaction*	Pruritis without rash or erythema or localized urticaria, diffuse maculopapular rash, dry desquamation	Generalized urticaria, angioedema or worse, vesiculation, moist desquamation, ulceration up to and including: exfoliative dermatitis; mucous membrane involvement; or Stevens-Johnson Syndrome, or erythema multiforme, or necrosis requiring surgery
Systemic infection	Any systemic infection.	Systemic infection requiring hospitalization.
Other systemic	No treatment required and no limitations or mild impairment of usual activities	Vigorous treatment, hospitalization usually required, immediate risk of death
Seizure		Any occurrence is a serious adverse event
Cancer		Any occurrence is a serious adverse event
Congenital Anomaly/Birth Defect		Any occurrence is a serious adverse event
Disability or Permanent Damage		Any occurrence is a serious adverse event
Hospitalization		Any occurrence is a serious adverse event
Life-threatening event		Any occurrence is a serious adverse event

Serious adverse event collection begins after the patient has signed informed consent and has undergone pterygium excision. If a patient experiences an SAE after signing informed consent, but prior to undergoing surgery, the event will be treated as unrelated to the study unless the investigator feels the event may have been caused by a protocol procedure. Adverse events (SAEs) occurring after a patient has received the last injection of the study drug will be collected for 30 days after the last dose of study drug, regardless of the investigator's opinion of causation. Thereafter, SAEs are not required to be reported unless the investigator feels the events were related to the study drug or a protocol procedure.

b. Adverse Event Reporting

Study personnel must alert the medical monitor of any **SAE** within 24 hours of investigator awareness of the event. Alerts issued via telephone are to be immediately followed with official notification on the Serious Adverse Event Reporting form (MOP). All serious or unexpected Adverse Events judged to be definitely, possibly, or probably related to study participation will be reported to the UCSF CHR (Committee on Human Research) within 5 working days of their occurrence. All reporting will be performed following CHR guidelines. The study physician must report new significant follow-up information for these events to the principal investigator immediately (i.e., no more than 24 hours after becoming aware of the information). New significant information includes the following:

- New signs or symptoms or a change in the diagnosis
- Significant new diagnostic test results
- Change in causality based on new information
- Change in the event's outcome, including recovery
- Additional narrative information on the clinical course of the event

c. Determination of Causality

Causality of the adverse event will be determined by the study investigators and the DSMB. Events will be determined to be one of the following:

- **Definitely Related:** if it is clear that the event was caused by study participation. A definitely related event has a strong temporal relationship and an alternative cause is unlikely.
- **Probably Related:** If there is a possibility that the event is likely to have been caused by study participation. The AE has a timely relationship to the study procedure(s) and follows a known pattern of response, but a potential alternative cause may be present.
- **Possibly Related:** If there is a reasonable possibility that the event might have been caused by study participation. A possibly related event may follow no known pattern of response and an alternative cause seems more likely. An event may also be considered possibly related if there is significant uncertainty about the cause of the event, or a possible relationship to study participation cannot reasonably be ruled out.
- **Unrelated:** The cause of the AE is known and the event is in no way related to any aspect of study participation.

Uncertain Causality: If there is *any* uncertainty regarding AE causality then the event must be assessed as possibly related to research participation and reported to the IRB as indicated.

d. Emergency Medical Contacts

Principal investigator: [name].

Email: [contact]

[contact]

e. Investigator Follow-Up:

The investigator will follow all unresolved treatment-related adverse event until the event has resolved to baseline grade or better, the event is assessed as stable by the investigator, new therapy is initiated, the patient is lost to follow-up, or the patient withdraws consent. Every effort will be made to follow all serious adverse events considered to be related to study drug or trial-related procedures until a final outcome can be reported.

During the study period, resolution of adverse events (with dates) should be documented on the patient's Adverse Event Log (MOP) and in the patient's medical record to facilitate source data verification. If, after follow- up, return to baseline status or stabilization cannot be established, an explanation will be recorded on the patient's Adverse Event Log.

f. Data Review

The DSMC will review of data from enrolled patients at bi-annual committee meetings. The discussion will include the number of patients and any significant adverse events. If necessary, the Study Coordinator will provide unmasked treatment assignment to the committee.

g. Interim Analysis

Interim analyses of efficacy are not planned for this study.

h. Early Stopping of the Study

Stopping for harm will be done at the judgment of the DSMC.

Committee

[name] ([contact])

[name] ([contact])

i. Loss to Follow up

All patients will be offered enrollment in the text-messaging appointment reminder service. Patients that do not show up for scheduled study visits will be contacted by the study coordinator the day following their visit via phone and offered rescheduling. If they are unable to be contacted that day, repeated attempts will be made weekly for 4 weeks to contact patients lost to follow up. Additional attempts will be made at the 6- and 12-month points.

XVII. TREATMENT STOPPING RULES

a. Discontinuation:

Patients who discontinue one of the study treatments due to intolerance or side effects will be observed to the end of the study period unless they are unwilling or unable to return.

In addition, the investigator will discontinue patients from the study drug in the following circumstances:

- The investigator decides that the patient should be withdrawn from the study. If a SAE occurs and the investigator deems stopping study therapy is necessary, the investigator will discontinue the study therapy and take appropriate measures.
- The patient or attending physician requests withdrawal of the patient from the study.
- The investigator or the study sponsor stops the study or stops the patient's participation in the study for medical, safety, regulatory, or other reasons consistent with applicable laws, regulations, and good clinical practice (GCP).
- The patient becomes pregnant or fails to use adequate birth control (for women with reproductive potential).
- The patient is noncompliant with study procedures.

When a subject withdraws before completing the study, the reason for withdrawal is to be documented in the Patient Dropout Form (MOP).

Study agents assigned to the withdrawn subject may not be assigned to another subject. Subjects who withdraw will not be replaced.

References

1. Pflugfelder SC. Prevalence, burden, and pharmacoeconomics of dry eye disease. The American journal of managed care 2008;14:S102-6.
2. The epidemiology of dry eye disease: report of the Epidemiology Subcommittee of the International Dry Eye WorkShop (2007). The ocular surface 2007;5:93-107.

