A Randomized, Controlled Trial to Evaluate the Role of Oral Azithromycin in the Treatment of Symptomatic Meibomian Gland Disease and its effect on the Ocular Surface Microbiome

NCT Number NCT03953118

Date: January 2, 2018

Principal Investigator: [name]
Co-Investigator: [name] PhD

i. Background and Significance

Dry eye syndrome (DES) is a persistent feeling of ocular discomfort that encompasses dryness, irritation, foreign body sensation and burning. In the United States, it is the most common non-refractive cause of visits to eye care providers¹, and has been shown to have a significant impact on quality of life of patients who suffer from this condition². It is not one disease state, but rather is composed of multiple different entities whose end stage results in the symptoms encompassed by DES. The most common cause of DES is Meibomian gland disease (MGD).³

The Meibomian glands are modified sebaceous glands that line the upper and lower eyelids and have orifices opening onto the eyelid margin.⁴ The secretory product of the Meibomian glands is a finely tuned mixture of lipids with high spreadability and low surface tension that coat the ocular surface and provide an evaporative barrier against aqueous tear loss.⁵ A change in the composition of the lipids can cause the tear film to become unstable, either breaking up prematurely or failing to spread properly after blinking, which leaves the underlying corneal epithelium exposed.⁶

Numerous treatments for MGD have been proposed, ranging from heating the glands⁷ to topical anti-inflammatories^{8, 9}, oral omega-3 fatty acids^{10, 11}, and topical¹² or oral^{13, 14} antibiotics. The role of topical anti-inflammatories as effective has been well-established, but the role of antibiotics is less clearly defined. Some clinicians advocate using antibiotics to reduce the burden of bacteria on the ocular surface¹⁵, but the utility of this has never been established¹⁶, nor have there been any causal relationship demonstrated between a bacterial pathogen and MGD¹⁷.

A competing theory for the use of antibiotics to treat MGD is that they exhibit an anti-inflammatory effect on the Meibomian glands, thereby improving the composition of secreted lipid. The macrolide and tetracycline antibiotics have been shown to have a anti-inflammatory effects in addition to their antimicrobial action.¹⁸ Azithromycin has also been shown to affect the lipid composition of cultured human Meibomian gland cells.^{19, 20}

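### Section XV takes the HD Analyzer reading (OSI, secondary outcome 8) last of five tests with no stated interval, so it is read on a tear film already handled; a minor, cheaply avoided source of possible noise

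*Combined protocol and SAP*

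**What the plan says.** Section XV opens with a rule on sequence: "The evaluation procedures should be performed in the order specified below to minimize disruption of the ocular surface". It then lists five procedures.

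1. Tear breakup time: "A dry fluorescein strip should be touched lightly to the tear meniscus". This item protects itself: "The tear breakup time should be measured prior to instillation of any anesthetic drops".
2. Meibomian gland grading: after the glands are inspected, "the glands will be expressed using the MGED, and meibum quality score will be assigned".
3. Schirmer testing, without anaesthetic: strips in both lower lids for 5 minutes, or less if a strip is fully wetted sooner.
4. SICCA scoring: a fluorescein drop, a wait of about 5 minutes, a corneal count, then a lissamine green strip wetted with proparacaine (30 seconds allowed) applied to the conjunctiva.
5. HD Analyzer, described as measuring light scatter at the ocular surface.

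The reason given for item 5 is optical: "As the tear film is the first surface that light encounters as it enters the eye", a disturbed tear film can affect what is measured. Its timing is given in one sentence: "Subjects will receive HD Analyzer measurements of the OSI (ocular surface index) at enrollment, 1 month, and 3 month timepoints per manufacturer instructions". No interval after item 4 is stated. Section VII lists change in OSI at 1 and 3 months as secondary outcome 8.

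**The concern.** A reading that the protocol links to the tear film comes after every test that touches, dyes or wets the eye or expresses the lid glands. Tear breakup time is kept ahead of anaesthetic drops and Schirmer testing is done without them, but OSI directly follows the proparacaine step and has no such protection. If the earlier tests disturb the tear film by an amount that differs from visit to visit in the same eye, change in OSI carries noise that an earlier reading would avoid. What is at stake is the precision of one of eight secondary outcomes.

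**Working it through.** **Position and exposure.** Manipulations before item 5, counted from Section XV: fluorescein strip (1) + gland expression (1) + Schirmer strip (1) + fluorescein drop and lissamine green with proparacaine (2) = 5. Stated contact or waiting times before the reading: Schirmer up to 5 min + fluorescein about 5 min + proparacaine 0.5 min = at most about 10.5 min. Stated interval between items 4 and 5: none.

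**How many readings.** Section IX recruits 19 per arm, so 19 × 2 = 38 patients, and 38 × 3 visits = 114 patient-visits. With the 16 per arm from the sample size calculation, 32 × 3 = 96. These figures count exposure; they do not measure harm.

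**Why the tear film could matter.** Section i says the gland secretion is a "mixture of lipids with high spreadability and low surface tension that coat the ocular surface" and that "A change in the composition of the lipids can cause the tear film to become unstable". Item 2 expresses those glands before OSI is read. Section XV attributes optical effects to tear-film disruption caused by the disease; it does not say that testing has the same effect. That step is an inference.

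**Which disturbance adds noise.** Write the observed OSI of eye i at visit t as

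Y(i,t) = T(i,t) + a(i) + b(t) + e(i,t)

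where T is the reading without prior handling, a(i) is a shift stable within the eye, b(t) is a shift common to both arms at that visit, and e(i,t) is the remainder. Change from enrollment is

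Y(i,1) − Y(i,0) = [T(i,1) − T(i,0)] + [b(1) − b(0)] + [e(i,1) − e(i,0)].

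- a(i) drops out of each eye's change. Differences between eyes in expressed meibum (Table 2) therefore do no harm if they are stable.
- b(1) − b(0) drops out of the difference between arm means.
- Only e remains. If it has variance s², independent across visits and of T, it adds 2s² to the variance of each change.

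**Could e be non-zero?** The protocol leaves four routes open: Schirmer contact time that may end before 5 minutes; a fluorescein wait given only approximately; an unstated delay between SICCA scoring and OSI; and meibum release that may change between visits (change in gland grading is itself secondary outcome 6).

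**Size.** The documents give no OSI effect size, no SD and no value for s², which may be zero. The only sample size calculation, in Section IX, concerns OSDI and cannot be carried over to OSI. No loss of power is computed.

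**The case against.** The strongest case against has four parts.

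- **No document says that testing alters OSI.** This stands: the size, the duration and even the existence of the effect would have to come from elsewhere.
- **The manufacturer instructions may set a wait or condition.** They, and the Manual of Procedures to which the protocol refers elsewhere, are not available here. This stands as a reason to check them. The phrase does not move the HD Analyzer from fifth place, and the protocol itself states no interval.
- **A fixed order is harmless because shifts cancel.** This is right for shifts stable within an eye and for shifts common to both arms at a visit. It does not cover within-eye variation across visits, which the loosely specified times permit.
- **The order does not contradict its stated aim.** A reader might infer that Section XV contradicts itself. That is too strong. The aim is to limit disruption of the ocular surface; moving the HD Analyzer, for which no contact, drop or dye is described, would not reduce what the other four tests do. It would only protect the OSI reading from them.

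A reader might also infer bias between arms, for instance because azithromycin could change what item 2 releases. The documents do not support this: the order is the same in both masked arms, and nothing states that released meibum shifts OSI, or in which direction.

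**Conclusion.** The point holds as a minor improvement to measurement. The plan prescribes an order in which a tear-film reading follows five manipulations with no stated interval, although the same test could be taken first at almost no cost. The possible consequence is added within-eye, between-visit noise in one of eight secondary outcomes, across all 114 planned patient-visits. Its size is unknown and may be nil. The conclusion rests on one assumption that the documents do not state: that dye, strips, gland expression or anaesthetic can alter OSI for at least a short time. No between-arm bias and no loss of power are shown. The primary outcome, a questionnaire score, is unaffected.

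**What to change.** In Section XV, make the HD Analyzer item 1, taken before any strip, drop, dye or gland expression at every visit, and renumber: HD Analyzer, tear breakup time, gland grading, Schirmer, SICCA. The relative order of the other four does not change. Before adopting this, check it against the manufacturer instructions that Section XV cites. If they require another position, state that position in Section XV with a fixed minimum interval after the preceding test.

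The cost is a small change to visit workflow, with no added patients, visits or tests. The change should be made before the first enrollment reading, because the conditions of that reading cannot be restored later.

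As a separate clerical tidy-up, the Section XIII table has rows for the other four procedures but none for the HD Analyzer. A row marked at all three visits would match the timing already given in Section XV.

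### The stool-count criterion for Serious diarrhea stops at 9 with nothing above it, so by count alone 10 or more stools is graded below 8-9

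*Combined protocol and SAP*

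**What the plan says.** Section XVI.a sorts each systemic event into a Non-Serious or a Serious column. For diarrhea, the Non-Serious column is a catch-all. The Serious column reads "Severe, bloody diarrhea or 8-9 loose stools in 24 hours" and continues "or orthostatic hypotension or at least a 2.5 kg weight loss resulting from diarrhea". The limbs are joined by 'or', so any one is enough.

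Other rows of the table are open at the severe end. Nausea is serious with "minimal food intake for 3 or more days or at least a 2.5 kg weight loss resulting from nausea", and muscle strength with "Objective weakness, function limited, or worse". Fever is serious at or above 103°F, and fatigue when normal activity falls by more than 50%.

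Further rows apply whatever the stool count. For hospitalization and for a life-threatening event the entry is "Any occurrence is a serious adverse event". The serious entry for other systemic events is "Vigorous treatment, hospitalization usually required, immediate risk of death".

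Under Section XVI.b the medical monitor must be alerted to any SAE "within 24 hours of investigator awareness of the event". Section XVI.a also has every adverse event, serious or not, recorded on the Adverse Event Reporting Form and entered in the patient's log.

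**The concern.** A seriousness rule should not move an event down a category as it gets worse. Here the count criterion switches on at 8 and off again after 9, and whatever it does not catch falls to the Non-Serious column.

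What is at stake is escalation, not recording. The 24-hour alert is tied to SAE status. Reporting to the CHR within 5 working days covers related events that are serious or unexpected, so a related case classed Non-Serious and judged expected would miss that route as well. Study drug is given weekly for 3 weeks (Section iii), and the DSMC meets twice a year (Section XVI.f). Committee review is therefore not a substitute for a prompt alert during treatment. The study drug is an oral antibiotic, and diarrhea has its own row in the table, so the plan itself treats the event as one to watch.

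**Working it through.** No sample-size or error-rate figure bears on this point. The check treats the row as a logical rule and applies it.

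**Rule as printed.** Serious = (severe, bloody diarrhea) OR (8-9 loose stools in 24 h) OR (orthostatic hypotension) OR (weight loss of at least 2.5 kg). Otherwise Non-Serious.

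**Classification by count alone** (no blood, orthostatic hypotension or 2.5 kg loss, and no hospitalization, life threat or other general serious-event row met):

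| Loose stools in 24 h | Count limb met? | Column |
|---|---|---|
| 1-7 | No | Non-Serious |
| 8-9 | Yes | Serious |
| 10 or more | No | Non-Serious |

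The sequence is Non-Serious, Serious, Non-Serious, so the literal rule does not rise steadily with severity.

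**Classification when another criterion is met.** With bloody diarrhea of the kind the cell describes, orthostatic hypotension, a 2.5 kg loss, hospitalization or a life-threatening event, 10 or more stools is Serious and the alert applies. The gap is therefore the 10-or-more group with none of these.

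**Comparison with the rest of the table.** The other numeric Serious limits are 3 or more days, at least 2.5 kg, at or above 103°F, and more than 50%. None has a ceiling. The fever row does contain a closed range, but in its Non-Serious cell with an open Serious category above it. The clinical scales in Section XV follow the same pattern: the top plugging grade in Table 2 is five or more glands, and the top SICCA staining grades are more than 100 and more than 30 dots. The diarrhea count is the one numeric Serious limit closed at the top. No general statement in the documents says that a listed range is a minimum.

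**Size.** Planned recruitment is 2 × 19 = 38 patients (Section IX). The documents give no rate of diarrhea at any stool count, so the expected number of affected cases cannot be calculated and may be zero.

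**The case against.** The strongest reply is that nobody would read the cell this way. A patient with 12 stools has already passed 8-9, and the cell opens with the word severe. The columns are plainly not exclusive bins: the Non-Serious catch-all literally includes 8-9 stools, and 103°F falls in both fever columns. Investigators must already use judgement, and the natural convention is to take the more serious column. The same literalism would stop SAE collection from ever starting, because Section XVI.a ties it to pterygium excision, which is not part of this trial.

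Much of this stands as a reason to call the point minor. It does not close the gap. Taking the more serious column settles an overlap, where both columns match. At 10 or more stools by count, only the Non-Serious column matches. The word severe is not clearly a criterion of its own: the vomiting row uses it as a label for what follows, and the headache row follows it with the defining condition. Two assessors could fairly class the same event differently. The pterygium wording is a separate defect affecting all SAEs, and correcting it would leave this cell unchanged.

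A reader might also infer more than the documents support:

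- **That the whole Serious definition is capped, so every patient with 10 or more stools misses the alert.** Only one of several alternative limbs is capped. The sickest patients are also likely to meet another limb or a general row.
- **That review of study therapy would be lost.** Section XVII.a does have a clause beginning "If a SAE occurs and the investigator deems stopping study therapy is necessary", but it also provides for discontinuation by investigator decision and at the request of the patient or attending physician, and for stopping participation on medical or safety grounds. None of these needs an SAE.
- **That a between-arm SAE comparison would be distorted.** Section VIII plans no such comparison.
- **That oversight would be blind.** Non-Serious events are still logged, and the DSMC discusses significant adverse events, not only serious ones.

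**Conclusion.** The point holds in a narrow form and is minor. As printed, the stool-count limb grades 10 or more stools below 8-9 for a patient who meets no other Serious criterion, and such a case would fall outside the 24-hour medical-monitor alert. It would still be recorded, and stopping therapy would still be open to the investigator.

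This rests on two assumptions: that assessors apply the printed range as written, and that the Manual of Procedures, which holds the reporting form and is not among the documents, does not already say how higher counts are classed. If either fails, the practical effect disappears and only the wording needs tidying.

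**What to change.** The sponsor should reconcile the diarrhea cell with the table's other numeric Serious thresholds so that counts above the printed range are not classed below it. This means removing the ceiling and leaving the plan's own lower number unchanged. No new threshold is needed. The Adverse Event Reporting Form in the Manual of Procedures should carry the same wording.

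The cost is one table cell and the matching form. The downside is that a few more events may be classed as SAEs and need the 24-hour alert; how many cannot be judged from the documents. The edit could be made together with correction of the surgical and injection wording elsewhere in Section XVI.a.
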